Studies have shown that the biphasic calcium phosphate (BCP) Straumann BoneCeramic® used for sinus floor elevations or alveolar ridge preservation can result similar bone changes to standard graft material (Bio-Oss®), 16,17 and can result in excellent survival and success rates of dental implants placed subsequently. Straumann BoneCeramic® consists of hydroxyapatite (HA) and β-tricalcium phosphate (β-TCP) in a 60:40 ratio, so that the HA acts as a scaffold for space maintenance while the β-TCP resorbs and supports bone regeneration. A new second generation macro- and microporous BCP (mean micropore diameter 1 µm) has been developed with an HA/TCP ratio of 10:90 and controlled microporosity, which may be an important factor in the osteoconductive capacity of calcium phosphate ceramics. 19 This material has demonstrated biocompatibility and osteoconductivity and is designed to act as a scaffold that allows cells to infiltrate the site of the defect for subsequent bone regeneration and is designed to provide substitute degradation, i.e. chemical/non-cellular dissolution of BCP in parallel with resorption by osteoclasts. Bone formation starts with an organic cellular matrix being formed by cells (including pre-osteoblasts) around the BCP particles. Preclinical data have indicated that in addition to direct bone deposition on the surface of the BCP particles, mineralization and ossification also occurs in the inter-granular spaces. This occurs as a result of calcium and phosphate, released by substitute degradation, that become embedded in the organic matrix,

Version 6.0 Page 13 of 47

similar to the process of ossification that occurs during osteogenesis; this is assumed to enable random bone formation throughout the defect.

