#### 7.9 Randomization

Subjects will be randomized either to the test group receiving Straumann® VivOss™ or comparator group receiving Geistlich Bio-Oss®. The master randomization list will be kept in a secure repository in the office of the Sponsor. The study centers have to contact the Sponsor by email or phone to request randomization of a subject, the Sponsor will send a randomization form including randomization details via email or fax. Although this study is not blinded, no access to the randomization list will be available to the study centre, the external Monitors, the subjects and the Straumann non-Clinical-Research project team.

Site/s of Biopsy

The site of biopsy in each sinus depends on the number of implants to be placed in the sinus. If more than one implant will be placed the most preferred site will be position 6, followed by position 5, followed by position 7, the least preferred position is position 4.

Version 6.0 Page 20 of 47

If more than one implant is placed, the investigator should take 2 biopsies following the preference list above. The second biopsy should be taken as backup in case the first biopsy cannot be evaluated.

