### 7.14 Biopsy

The bone biopsies are retrieved in both the test and the comparator group.

The bone biopsies will be retrieved from the central part of the dental implant osteotomy and will be processed together with the trephine burr. The biopsies will be immersed and fixed in buffered formalin. Further processing of the biopsy and evaluation of the histologies is described in detail in a separate technical procedure protocol. The biopsy-samples will be labelled with:

- Patient number
- Position (FDI)

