#### 10 Statistical Procedures

The statistical analysis principles described below will be supplemented by a detailed statistical analysis plan (SAP) which will be written after the first patients have performed visit 2 and will be finalized, based on the findings of the data review meeting, before the database is locked.

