### 10.2 Statistical Hypotheses

The primary endpoint of this study is the histological evaluation of the ratio of newly formed bone to residual bone graft in *Straumann*® *VivOss*™ compared to *Geistlich Bio-Oss*® at visit 4 (6 month ± 7 days, after sinus elevation).

In this study the following hypothesis will be tested

Straumann® VivOss™ combined with Bio-Gide shows a significantly higher ratio of newly formed bone to residual bone graft compared to Geistlich Bio-Oss® combined with GeistlichBio-Gide at visit 4 (6 month ± 7 days, after sinus elevation).

- T: Test Group
- C: Comparator Group

Testing for Superiority (based on the per protocol (PP) data set):

 $H_{0S}$ : T = C

 $H_{1S}$ :  $T \neq C$ 

 $H_{0S}$  is the null hypothesis, claiming that there is no difference in the true mean of ratio of newly formed bone to residual bone graft after 6 months between the test group and the negative control group

H1S is the alternative hypothesis claiming that the true mean change of ratio of newly formed bone to residual bone graft after 6 months is unequal in the two treatment groups; either higher or lower in the test group than in the negative control group.

- T is the true mean at 6 months of the ratio of newly formed bone to residual bone graft in the test group.
- C is the true mean at 6 months of the ratio of newly formed bone to residual bone graft in the control group.

The secondary efficacy variables in this clinical study are:

- Survival rate of study implants evaluated at visit 6 (initial implant loading)
- Success rate of study implants evaluated at visit 6 (initial implant loading)

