### 10.3 Sample Size Calculation

Sample size calculations were performed for a clinical relevant difference between test and comparator across a given range of standard deviations, and with the two-sided unpaired t-test under a significance level  $\alpha = 5\%$  and with a power  $\beta = 80\%$ .

a) Sample Size for Test to Show Superiority of Test Group vs. Control Group

Version 6.0 Page 30 of 47

Based on a recent pre-clinical study a difference of the means of the ratio of newly formed bone to residual bone graft of approximately 0.4 can be expected in favour of the test treatment compared to the control. Considering a common standard deviation of 0.5, 25 subjects per group would be necessary to confirm this clinically relevant difference statistically.

Table 1: Sample size for superiority based on  $\Delta = 0.4$ :

Common SD [mm]	0.425	0.45	0.475	0.5	0.525	0.55	0.575
n Test	18	20	23	25	28	30	33
n Control	18	20	23	25	28	30	33

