### 13.3 Protocol Amendments

Once the first subject has entered the study, protocol changes will be kept to a minimum. Only those changes that are deemed essential to the successful completion of the protocol will be considered.

If changes to the protocol are proposed, they shall be discussed with the study manager in a timely manner. IEC approval and Authority approval is required for any change in the protocol or in the informed consent that may affect the scientific soundness of the study or the right, safety, or welfare of the. The change in the protocol can not be implemented until the approvals are obtained. Once the investigator and the Sponsor have accepted the changes, a written amendment to the protocol will be sent the investigator for signature.

Requests for clarification statements to the protocol shall be discussed with the study monitor. The clarification statements will be sent to each investigator and will be kept in the appropriate file.

Version 6.0 Page 37 of 47

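### Does the primary ratio need a new analysis rule for biopsies in which no graft remains?

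*Combined protocol and SAP*

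**What the plan says.** Section 10.2 defines the primary comparison as a difference in true means of a quotient, per protocol set, at 6 months: "T is the true mean at 6 months of the ratio of newly formed bone to residual bone graft in the test group". It names no test. The only test named is in the sample-size section (10.3), where the calculation is done "with the two-sided unpaired t-test under a significance level" of 5%. The planned difference is 0.4. "Considering a common standard deviation of 0.5", 10.3 arrives at 25 subjects per group.

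Four other places bear on the point:

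- Section 2 says the test material "is designed to provide substitute degradation, i.e. chemical/non-cellular dissolution of BCP in parallel with resorption by osteoclasts".
- Section 7.9 asks for two biopsies when more than one implant is placed: "The second biopsy should be taken as backup in case the first biopsy cannot be evaluated". It does not define when a biopsy counts as not evaluable.
- Section 7.14 hands the laboratory detail to another document: "Further processing of the biopsy and evaluation of the histologies is described in detail in a separate technical procedure protocol".
- Section 10 announces a detailed SAP, which "will be finalized, based on the findings of the data review meeting, before the database is locked".

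**The concern.** A quotient with a zero denominator cannot be averaged. If one test biopsy shows new bone and no residual graft, the test-arm mean does not exist until someone adds a rule. Because the test graft is designed to dissolve and be resorbed, the problem would fall mainly on one arm and on its best results.

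The existing rules could then act on that biopsy in unwanted ways. It could be called not evaluable and replaced by the backup core, which may still hold graft. A subject with a single implant has no backup, so the subject could leave the per protocol set and be replaced under section 8.4 while recruitment is open. Either route removes the outcome the product is meant to give and shrinks the estimated difference.

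A biopsy with almost no graft poses a different problem. Its ratio is defined but can be very large, and one such value can inflate the SD enough to hide the planned difference. The trial is open label, and the SAP is settled after a data review meeting whose blinding is not described, so a rule chosen at that point might be chosen with the data in view.

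**Working it through.** **Inputs.** From 10.3: difference 0.4, common SD 0.5, two-sided 5%, power 80%, 25 per arm. Assumed, because the documents do not give them: control mean 1.0 (hence test mean 1.4), lognormal ratios, and the frequency of zero-graft biopsies.

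**1. The plan's own figure.** n = 2(1.960 + 0.842)² × 0.5² / 0.4² = 24.5, so 25 per arm. The same formula reproduces every cell of Table 1 (18, 20, 23, 25, 28, 30, 33). Exact t-test power at 25 per arm is 79.2%. The sample size is not in dispute.

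**2. How often a zero could appear.** P(at least one in 25) = 1 − (1 − p)²⁵. For assumed rates p of 1%, 2% and 5% this is 22%, 40% and 72%. No passage supports any particular p.

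**3. Cost of leaving zero-graft test biopsies out** (simulation, lognormal; t-test power with none left out is 79%):

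| Test biopsies left out | Which ones | Difference | t-test power |
|---|---|---|---|
| 1, 2, 3 | random | about 0.40 | 78%, 77%, 76% |
| 1, 2, 3 | exactly the highest | 0.35, 0.31, 0.28 | 72%, 65%, 57% |

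The loss is about 1 to 3 points in the first case and about 7 to 22 points in the second.

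**4. Cost of swapping in the backup core.** If the backup is treated as an independent draw from the other test values, power for one, two or three swaps is 73%, 66% and 60%. But the backup comes from the same patient, sinus and graft. With an assumed within-patient correlation of 0.5, power is 77%, 74% and 71%; with 0.8 it is 78%, 77% and 76%.

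**5. Near-zero graft.** Put one test ratio at 10 and leave the other 24 as planned.

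- Difference = 0.4 + (10 − 1.4)/25 = 0.744.
- Test variance ≈ [23 × 0.25 + 0.96 × 8.6²]/24 ≈ 3.20.
- Standard error = √[(3.20 + 0.25)/25] = 0.371.
- t ≈ 0.744/0.371 = 2.00, against a critical value of 2.01 on 48 degrees of freedom, so power is about 50%.

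With one ratio at 15, t ≈ 0.944/0.562 = 1.68. Simulated power is 50% and 10%. A single ratio of 3 to 6 leaves power at 79 to 85%.

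Under the planning model itself, such values hardly occur. The log-scale variance is ln(1 + 0.25/1.96) = 0.120 and the log-scale mean is 0.276. So z for a ratio of 7 is (1.946 − 0.276)/0.346 = 4.82, and P ≈ 7 × 10⁻⁷ per biopsy, or about 2 in 100,000 trials. Harmful outliers need a separate mechanism that the documents do not describe.

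**6. Would a prescribed change of test help?** Consider a rule that uses the unequal-variance t-test if every ratio is defined and the rank-sum test if any is not.

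- Near-zero cases: every ratio is defined, so the unequal-variance t-test applies. Its power is 46% against 50% for the planned t-test (one ratio of 10) and 7% against 10% (one of 15). The rank-sum figure of 91% in these cases would not be the primary result.
- Identical arms: type I error is 4.3 to 5.2%.
- Equal means of the defined ratios, SD 1.0 against 0.5, and 2 to 5% zero graft in both arms: 15 to 17% of trials are significant in favour of the less variable arm, because the rank test does not compare means.

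**The case for a change.** The strongest case for acting is that the gap is real, foreseeable and one-sided, and that a few sentences would close it before any biopsy is read. If the zero-graft rate were even 2%, a trial of this size would have a 40% chance of meeting the problem, and a rule chosen afterwards could be influenced by the data. The power losses in the unfavourable scenarios are also reproducible.

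Much of this stands. The ratio is undefined at zero graft, the text reviewed has no rule, and the backup criterion is not spelled out. What does not carry over is the step from there to a defect in the plan.

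- The plan sends both histology evaluation and analysis detail to documents that were not available here. A smallest countable graft area and the meaning of an evaluable core belong in those documents, so their absence from the protocol does not show that they are absent from the plan.
- The natural reading of the backup rule is a technically unusable core. A core showing new bone and no graft has been read successfully.
- The larger losses need zero graft to coincide with the very highest ratios, or an isolated extreme value that the planning assumptions make very unlikely.
- Leaving out or swapping such biopsies works against the sponsor's own product. No route to a false claim of superiority has been shown for either.
- Section 10.1 already requires the median, quartiles, minimum and maximum by arm, so extreme ratios would be visible.

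**Conclusion.** No change to the plan follows. The protocol leaves a rule unwritten; it does not state one that gives a wrong answer. An analyst would be expected to keep a core with new bone and no graft, reserve the backup for technical failures, fix one rule for zero or near-zero graft that does not depend on the data, and report the number of such biopsies per arm. New bone as a share of new bone plus graft is a natural supportive measure. All of this fits in the SAP and histology protocol that the plan already provides for, and the primary endpoint stays as it is.

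The one substantive alternative, a data-dependent switch from a test of means to a rank test, is a debatable trade. It does slightly worse than the planned t-test in the near-zero cases and changes the hypothesis whenever a single zero appears. Writing it into the protocol could also need the approvals in section 13.3 ("IEC approval and Authority approval is required for any change in the protocol" affecting scientific soundness).

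The size of the issue rests on assumptions: lognormal ratios with means 1.4 and 1.0, SD 0.5, and one to three affected test biopsies. On that basis, leaving them out costs between about 1 to 3 points of power (random) and about 7 to 22 points (highest ratios). The conclusion would weaken if neither the SAP nor the histology protocol dealt with a zero denominator and such biopsies proved common; the documents do not settle either point.

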### 10.3 Sample Size Calculation

Sample size calculations were performed for a clinical relevant difference between test and comparator across a given range of standard deviations, and with the two-sided unpaired t-test under a significance level  $\alpha = 5\%$  and with a power  $\beta = 80\%$ .

a) Sample Size for Test to Show Superiority of Test Group vs. Control Group

Version 6.0 Page 30 of 47

Based on a recent pre-clinical study a difference of the means of the ratio of newly formed bone to residual bone graft of approximately 0.4 can be expected in favour of the test treatment compared to the control. Considering a common standard deviation of 0.5, 25 subjects per group would be necessary to confirm this clinically relevant difference statistically.

Table 1: Sample size for superiority based on  $\Delta = 0.4$ :

Common SD [mm]	0.425	0.45	0.475	0.5	0.525	0.55	0.575
n Test	18	20	23	25	28	30	33
n Control	18	20	23	25	28	30	33

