### 4.4 Number of Subjects

This study will be performed in two clinical centres, one in Germany and one in Switzerland; these centres are expected to recruit 50 subjects in total, 25 subjects in test group, 25 subjects in control. Planned subject recruitment period is 3 months. The recruitment is competitive. Recruitment will be stopped as soon as recruitment is complete.

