### 4.5 Study Duration

The primary endpoint will be assessed 6 months  $\pm$  7 days after sinus floor elevation. The entire study duration for each enrolled subjects is 9-14 months (screening to last visit).

The entire study duration from first patient in until last patient out will be approximately 17 months.

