### 5.4 Treatment Groups

In total 50 subjects will be randomize equally into test or control group (25 patients in each group).

The subjects in the test group receive sinus floor elevation with HA/TCP 10:90 (*Straumann*® *VivOss*™) via a lateral approach. In the comparator group, subjects receive sinus floor elevation with demineralized bovine mineral (Bio-Oss®) via a lateral approach.

Both groups follow the same schedule of assessments.

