### 8.4 Subject Replacement Policy

For any subject who for any reason drops out of the per-protocol population a new subject with a new number should be allocated if the recruitment period is ongoing.

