### 10.4 Populations for Analysis

### 10.4.1 Per Protocol Set (PP)

Randomized subjects who terminated the study and in whom no major protocol violations have been observed.

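### The 25 per group called necessary for 80% power is also the number randomised, although the primary test uses the per-protocol set and later losses are not replaced

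*Combined protocol and SAP*

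**What the plan says.** Section 10.3 plans for a two-sided unpaired t-test at 5% with 80% power, a mean difference of 0.4 and a common SD of 0.5, and concludes that "25 subjects per group would be necessary to confirm this clinically relevant difference statistically". Table 1 gives 18 to 33 per group for SDs from 0.425 to 0.575.

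The same number is carried into the recruitment target without change. Section 5.4 says: "In total 50 subjects will be randomize equally into test or control group (25 patients in each group"; section 4.4 agrees.

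The analysis set is narrower than the randomised set. Section 10.2 announces "Testing for Superiority (based on the per protocol (PP) data set", and section 10.4.1 defines that set as "Randomized subjects who terminated the study and in whom no major protocol violations have been observed".

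On replacement, section 8.4 provides that for a subject leaving the PP population "a new subject with a new number should be allocated if the recruitment period is ongoing". Section 4.4 says "Planned subject recruitment period is 3 months" and "Recruitment will be stopped as soon as recruitment is complete". Section 4.5 places the primary assessment 6 months ± 7 days after surgery.

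**The concern.** The sample-size formula returns the number of subjects needed in the analysis. Here that number is also the number randomised, while the PP set can only be the same size or smaller. Subjects can leave it by withdrawal (8.3), by loss to follow-up (8.5) or through a major protocol violation, a term the protocol does not define.

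Replacement covers only part of this, because recruitment is planned to close well before the first biopsy is due. A subject who withdraws after recruitment closes, or who has no usable biopsy at Visit 4, is not replaced.

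The stake is how the result is read. At the planning values, 80% is not reached by the named test even with complete data, and each unreplaced loss lowers the power further. If the trial is non-significant, readers would judge it against a power that the design did not have.

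**Working it through.** **Inputs.** Section 10.3: difference 0.4, SD 0.5, two-sided 5%, power 80%, unpaired t-test. Sections 4.4 and 5.4: 25 + 25 randomised. Section 4.4: 3 months of planned recruitment. Section 4.5: biopsy at 6 months ± 7 days. Loss rates of 10% and 20% are assumptions.

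**1. Reproducing the plan's figure.** By the normal approximation, n per group = 2 × [SD × (1.960 + 0.842) / 0.4]². At SD 0.5 this is 24.53, rounded up to 25. The whole of Table 1 follows:

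| SD | 0.425 | 0.45 | 0.475 | 0.5 | 0.525 | 0.55 | 0.575 |
|---|---|---|---|---|---|---|---|
| Raw n | 17.72 | 19.87 | 22.14 | 24.53 | 27.04 | 29.68 | 32.44 |
| Table 1 | 18 | 20 | 23 | 25 | 28 | 30 | 33 |
| Smallest n with t-test power of at least 80% | 19 | 21 | 24 | 26 | 29 | 31 | 34 |

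Table 1 is the raw value rounded up, so it holds no hidden inflation for loss. The t-test needs one more per group in every column.

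**2. Power of the t-test with fewer PP subjects.** The noncentrality is (0.4 / SD) / √(1/n₁ + 1/n₂), with n₁ + n₂ − 2 degrees of freedom. For 25 + 25 at SD 0.5 it is 0.8 / √0.08 = 2.828 on 48 degrees of freedom, with critical value 2.011 and power 79.1%. At SD 0.5:

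| PP subjects | t-test | Normal approximation |
|---|---|---|
| 25 + 25 (no loss) | 79.1% | 80.7% |
| 24 + 25 (one lost) | 78.3% | 79.9% |
| 24 + 24 (two lost) | 77.4% | 79.1% |
| 22 + 23 (10% lost) | 74.6% | 76.5% |
| 20 + 20 (20% lost) | 69.3% | 71.6% |

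**3. Ends of the plan's own SD range (t-test).**

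| SD | No loss | 10% lost | 20% lost |
|---|---|---|---|
| 0.425 | 90.3% | 87.0% | 82.6% |
| 0.575 | 67.4% | 62.6% | 57.3% |

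The design absorbs a 20% loss at the low end of the range, but not at its planning value of 0.5.

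**4. Timing of replacement.** The earliest Visit 4 is 6 months minus 7 days after the first surgery, about 5.8 months, against 3 months of recruitment. On that timetable every biopsy falls after replacement has ended. If surgeries are spread evenly over the 3 months (an assumption), a subject has on average 1.5 of the 6 pre-biopsy months inside the recruitment period. About 4.5/6 = 75% of pre-biopsy follow-up then also lies outside it. The total duration of about 17 months in 4.5 equals 3 months of recruitment plus the 14-month maximum per subject, which leaves no room for late replacements.

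**The case against.** The strongest reply is that the arithmetic is sound by the method used: Table 1 reproduces in full, and one extra subject per group is only the difference between two standard formulas. This is right. The defect is a missing planning step and a power statement that depends on it, not a miscalculation.

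Second, the protocol does handle loss. Section 8.4 is keyed to the PP population, so the randomised total may exceed 50. A membrane defect is found before randomisation (4.3), so on the wording of 5.4 it does not use up one of the 50, although the synopsis speaks of 50 enrolled, which is less clear. Section 7.9 provides a backup biopsy where more than one implant is placed. If recruitment overran, replacement would last longer. All of this reduces the loss, but none of it covers a subject who withdraws, is lost or has a major violation after recruitment closes.

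Third, the inputs are soft. The difference is given only as approximate and comes from a pre-clinical study. With 25 + 25 and SD 0.5, moving it to 0.39 or 0.41 gives t-test power of 77.1% or 81.1%, a larger shift than one lost subject causes. This stands: one or two losses hardly matter, and the shortfall becomes material only at roughly 10% to 20%, rates that the documents neither support nor exclude.

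Finally, neither the treatment estimate nor the type I error is touched by the power calculation. That is true of this point and limits its weight.

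**Conclusion.** The concern holds. Twenty-five per group is both the calculated requirement and the number randomised, the primary test uses a subset, no loss allowance is stated, and replacement on the planned timetable ends before any biopsy is due. At a difference of 0.4 and SD 0.5, the named t-test has 79.1% power at best with 25 per group in the PP set, about 75% at 10% loss and about 69% at 20% loss.

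These figures assume losses unrelated to outcome, split about equally between groups, and recruitment closing as planned. They do not depend on whether a subject lost after a valid biopsy stays in the PP set. The wording of 10.4.1 leaves that open, since the study termination form is also used for screening failures (8.2) and for subjects lost to follow-up (8.5). The exclusive reading would add losses up to Visit 6.

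The statement of power should be corrected. The point does not invalidate the design.

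**What to change.** In section 10.3, reword the conclusion so that the 25 per group refers to subjects in the PP set and is labelled as a normal-approximation figure. Then add text along these lines:

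> No allowance for loss is included. With 25 per group randomised and SD 0.5, t-test power is about 79% if all 50 are in the PP set, 75% at 10% loss and 69% at 20% loss (assumed rates). At SD 0.425 it is 90, 87 and 83%; at SD 0.575 it is 67, 63 and 57%. Replacement under 8.4 does not cover losses arising after recruitment closes, and the backup biopsy in 7.9 helps only where more than one implant is placed.

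Add a note to Table 1 that it uses the normal approximation and that the t-test needs one more per group in each column. The table entries, the 25 per group and sections 8.4, 10.2 and 10.4 stay as they are.

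The cost is a few lines of text and no additional subjects. It recovers no power, and the stated power becomes slightly less favourable. Protecting the power would require inflation: to keep 25 in the PP set, 25/0.9 = 27.8, so 28 per group at 10% loss, or 25/0.8 = 31.25, so 32 per group at 20% loss. Starting from the t-test requirement of 26, the figures are 29 and 33. That is a larger change and is not needed to make the present text accurate.
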